3.2 Data Monitoring Committee

The study will have a Data Monitoring Committee (DMC) that will include key investigators and sponsor personnel. The DMC will review both safety and efficacy data after the first 20 patients have been enrolled and completed the first cycle of treatment, and then approximately every 6 months, or earlier as needed, throughout the study.

3.3 Removal of Patients from Therapy or Assessment

A patient must be discontinued from protocol-prescribed therapy if any of the following apply:

- Consent withdrawal for any reason at the patient's own request, or at the request of their legally authorized representative (where acceptable according to national law and/or local regulations);
- Progression of patient's underlying cancer per RECIST v1.1, or modified RECIST v1.1/PCWG3 guidelines for prostate cancer, as assessed by the investigator, unless the patient continues to derive clinical benefit from the study drug(s) according to the investigator, the investigator has consulted with the sponsor's medical officer or designee, and the patient has provided additional consent for treatment beyond progression at the next study visit;
- Any event, adverse or otherwise, that, in the opinion of the investigator, would pose an unacceptable safety risk to the patient;
- An intercurrent illness that, in the opinion of the investigator, would affect assessments of the clinical status to a significant degree and requires discontinuation of therapy;
- Noncompliance by the patient with protocol-mandated procedures;
- Study termination; or
- A positive pregnancy test at any time during the study.

Discontinuation of treatment does not necessarily indicate study discontinuation for a patient. Samples collected for research will continue to be used unless the patient explicitly withdraws consent for their use. Information that is collected while the patient has consented to be in the study cannot be withdrawn. Details are provided in the Informed Consent Form (ICF).

[figure not shown]
If the patient withdraws consent to continue in the study or discontinues the study for another reason it will be documented on the appropriate eCRF. A patient may withdraw consent to participate in an additional or optional part of a study that has a corresponding consent (ie, optional tumor biopsy) yet continue to participate and be treated/followed in the main part of the study.

The sponsor may discontinue the study early for any of the reasons noted in [Section 10.6](#).

3.4 Study Schema

The study schema in [Figure 1](#) summarizes the treatment design of the study.

Figure 1. Study Schema

Abbreviations: BID = twice a day; BRCA1/2m = BRCA1 or BRCA2 mutated; CID1 = Cycle 1, Day 1; CRPC = castration-resistant prostate cancer; ECOG = Eastern Cooperative Oncology Group performance status; gBRCA = germline BRCA; HER2 = human epidermal growth factor receptor 2; LA = locally advanced; PCWG3 = Prostate Cancer Working Group Guidelines Version 3; RECIST = Response Evaluation Criteria in Solid Tumors; SoC = standard of care.

3.5 End of Study

Upon formal closure of the study, individual patients who are continuing to benefit from treatment with rucaparib at the time of study closure, and who do not meet any of the criteria for withdrawal, will have the option of receiving rucaparib via another access mechanism. In addition, individuals who are continuing in LTFU may transition to have their LTFU and scans, if applicable, captured via another mechanism.

4 STUDY POPULATION

4.1 Number of Patients and Sites

The total enrollment planned for this study is approximately 220 patients. There will be approximately 20 study sites in the US.

4.2 Inclusion Criteria

Eligible patients must meet the following inclusion criteria:

1. Have signed an Institutional Review Board (IRB)/Independent Ethics Committee (IEC) approved informed consent form prior to any study-specific evaluation.
2. Be ≥ 18 years of age at the time the informed consent is signed.
3. Have an unresectable, locally advanced (primary or recurrent) or metastatic solid tumor and have relapsed/ progressive disease as confirmed by radiologic assessment.
4. Have measurable disease as defined by RECIST v1.1 ([Appendix 2](#)) or modified RECIST v1.1 and PCWG3 criteria ([Appendix 3](#)) for prostate cancer. A measurable tumor lesion in a previously irradiated site is acceptable if subsequent progression has been demonstrated in that lesion.
5. Have a deleterious mutation (germline or somatic) in BRCA1, BRCA2, PALB2, RAD51C or RAD51D (Cohort A) or a deleterious mutation (germline or somatic) in BARD1, BRIP1, FANCA, NBN, RAD51 or RAD51B (Cohort B). Mutations must be identified by either a local or central laboratory that is certified per Clinical Laboratory Improvement Amendments (CLIA) regulations.
 - a. Mutations may be identified in a tumor tissue, blood, or saliva sample. For a local laboratory test result, the classification of the mutation as deleterious must be documented in the patient's medical record. Variants of uncertain significance or benign variants will not be eligible for enrollment into the trial.
 - b. Patients with EOC, FTC, or PPC must have a deleterious PALB2, RAD51C or RAD51D mutation (or deleterious mutation in another HRR gene, listed in [Appendix 1](#)). Patients with a deleterious BRCA1 or BRCA2 mutation are not eligible.
 - c. Patients with mCRPC must have a deleterious PALB2, RAD51C or RAD51D mutation (or deleterious mutation in another HRR gene, listed in [Appendix 1](#)). Patients with a deleterious BRCA1 or BRCA2 mutation are not eligible.
 - d. Human epidermal growth factor receptor (HER2) negative breast cancer patients with a deleterious germline BRCA1 or BRCA2 mutation are not eligible, unless the use of both olaparib and talazoparib is contraindicated. Breast cancer patients with somatic BRCA mutations are eligible, as are HER2+ patients with deleterious somatic or germline mutations in any of the 11 genes listed in [Appendix 1](#). HER2 negative patients with a deleterious mutation in any non-BRCA HRR gene listed in [Appendix 1](#) are eligible.
6. Have received at least 1 line of available therapy(ies) with treatment demonstrated to have a survival benefit in the relevant tumor type or, in the absence of any OS-extending treatment, have received at least 1 standard-of-care treatment regimen.

- a. A treatment regimen that is held for reasons other than disease progression and subsequently resumed at a later date with no other intervening systemic anti-cancer therapy is considered 1 treatment regimen.
- b. Patients with EOC, FTC, or PPC must have received 2 prior lines of platinum-based chemotherapy and:
 - i. Had documented treatment-free interval of ≥ 6 months following the first platinum-based chemotherapy regimen received; and
 - ii. Had either platinum-sensitive or platinum-resistant disease (progression-free interval [PFI] ≥ 1 month after last dose of platinum). Patients with platinum-refractory disease (ie, whose disease progressed during or within 1 month of completing treatment with their most recent platinum-based therapy) are excluded.
- c. Patients with locally advanced or metastatic endometrial cancer, excluding uterine carcinosarcoma, must have received at least 1 line of platinum-containing therapy but no more than 2 prior chemotherapy-based regimens (eg, carboplatin/cisplatin, taxanes, doxorubicin, ifosfamide, topotecan or other chemotherapy regimens recommended by regional guidelines). Hormonal therapy, immunotherapy, mechanistic target of rapamycin [mTOR] inhibitors, anti-vascular endothelial growth factor [VEGF] or anti-HER2 therapy are not counted towards lines of therapy. Patients must not have had radiologic disease progression within 3 months of initiating platinum-containing chemotherapy, with a best response of SD or better.
- d. Patients with locally advanced or metastatic cervical cancer must have received at least 1 line of platinum-containing therapy, but no more than 2 prior chemotherapy-based regimens (including carboplatin/cisplatin, taxanes, topotecan, other chemotherapy regimens recommended by regional guidelines). Immunotherapy or anti-VEGF therapy are not counted towards the prior treatment lines. Patients must not have had radiologic disease progression within 3 months of initiating platinum-containing chemotherapy, with a best response of SD or better.
- e. Patients with either ovarian or uterine carcinosarcoma are restricted to 1 line of platinum-containing therapy and must not have had radiologic disease progression within 3 months of initiating platinum-containing chemotherapy, with a best response of SD or better.
- f. Patients with breast cancer:
 - i. Triple-negative breast cancer (TNBC) patients must have received no more than 2 prior lines of chemotherapy for metastatic disease. Patients may have previously received radiation therapy and 1 line of immunotherapy. Prior platinum as potentially curative treatment for prior cancer (eg, ovarian) or as adjuvant or neoadjuvant treatment for breast cancer is allowed; however, patients must not have progressed during treatment.
 - ii. All other breast cancer patients with tumors other than TNBC must have received no more than 2 prior chemotherapy regimens for locally advanced and/or metastatic disease, with no limit on prior hormonal therapies or targeted anticancer therapies such as mTOR inhibitors or cyclin-dependent kinase (CDK) 4/6 inhibitors (other than PARP inhibitors). Patients who have received

platinum in the adjuvant or neoadjuvant setting are eligible; however, subjects must not have progressed during treatment.

- g. Patients with mCRPC must have received prior androgen-receptor (AR)-targeted therapies (such as abiraterone acetate, enzalutamide, apalutamide, or investigational AR-targeted agent; 1 to 2 AR-directed agents allowed) and may not have received more than 2 lines of taxane for mCRPC.
- h. Patients with pancreatic cancer must have received no more than 2 prior chemotherapy-based regimens for locally advanced or metastatic disease and are eligible as long as they did not have radiologic disease progression during treatment with or within 3 months of receiving platinum-containing chemotherapy and have a best response of SD or better.
 - i. Neoadjuvant/adjuvant chemotherapy will not be counted as a treatment regimen if disease progression occurred ≥ 6 months following completion of chemotherapy. If disease progression occurred < 6 months following completion of chemotherapy, the regimen will be counted.
- i. Patients with gastric or esophageal cancer must have received no more than 2 prior chemotherapy-based regimens for locally advanced or metastatic disease and are eligible as long as they did not have radiologic disease progression during treatment with or within 3 months of receiving initiation of platinum-containing chemotherapy and have a best response of SD or better.
 - i. Neoadjuvant/adjuvant chemotherapy will not be counted as a treatment regimen if disease progression occurred ≥ 6 months following completion of chemotherapy. If disease progression occurred < 6 months following completion of chemotherapy, the regimen will be counted.
- j. Patients with colorectal cancer must have received no more than 2 prior chemotherapy-based regimens for locally advanced or metastatic disease and are eligible as long as they did not have radiologic disease progression during treatment with or within 3 months of initiation of platinum-containing chemotherapy and have a best response of SD or better.
 - i. Neoadjuvant/adjuvant chemotherapy will not be counted as a treatment regimen if disease progression occurred ≥ 6 months following completion of chemotherapy. If disease progression occurred < 6 months following completion of chemotherapy, the regimen will be counted.
- k. Patients with locally advanced or metastatic bladder cancer must have received 1 or 2 prior treatment lines (eg, cisplatin- or carboplatin-containing therapy, immune checkpoint inhibitor) for locally advanced resectable or metastatic disease. Patients who have received platinum-containing chemotherapy should not have radiologic disease progression within 3 months of initiation of platinum-containing chemotherapy and must have a best response of SD or better.
 - i. Neoadjuvant and/or adjuvant treatment for muscle invasive disease will be considered a treatment regimen if radiologic disease progression occurred within 12 months from the completion of treatment.
 - ii. No more than 1 prior platinum-containing chemotherapy regimen for advanced disease is permitted. A change of platinum chemotherapy within the same

treatment regimen will be considered 1 prior platinum-containing chemotherapy. Platinum-containing chemotherapy given as radio-sensitization combined with radiation therapy to control locally advanced disease will not be considered as a prior regimen of systemic therapy.

- iii. For patients who have never received platinum, the patient must currently be ineligible for cisplatin treatment.
1. Patients with metastatic non-small cell lung cancer (NSCLC) must have received no more than 2 prior lines of chemotherapy, including one line of platinum-containing therapy. Immunotherapy or targeted therapy (such as epidermal growth factor receptor [EGFR] inhibitor, c-ros oncogene [ROS] inhibitor, anaplastic lymphoma kinase [ALK] inhibitor or B-rapidly accelerated fibrosarcoma gene [BRAF] inhibitor) are permitted and do not count towards these prior lines.
 - i. Neoadjuvant/adjuvant chemotherapy after primary resection will not be counted as a treatment line if disease progression occurred ≥ 6 months following completion of chemotherapy. If disease progression occurred < 6 months following completion of chemotherapy, the line of therapy will be counted.
 - ii. No more than 1 prior platinum-containing chemotherapy line for advanced disease is permitted. A change of platinum chemotherapy within the same treatment regimen will be considered 1 prior platinum-containing chemotherapy. Patients must not have had radiologic disease progression within 3 months of initiating platinum-containing chemotherapy and must have best response of SD or better.
 - iii. Platinum-containing chemotherapy given as radio-sensitization combined with radiation therapy to control locally advanced disease will not be considered as a prior regimen of systemic therapy.
 - iv. Prior combined chemotherapy and radiotherapy is permitted provided the patient has measurable disease outside the radiation field or disease in the irradiated field has progressed.
- m. Patients with all other tumor types not mentioned above must have received 1, but no more than 3, lines of chemotherapy. In the rare circumstance where chemotherapy is not indicated / considered to be a preferred / recommended standard-of-care treatment for a given tumor type, an alternative therapy (eg, targeted therapy or immunotherapy) may meet the requirement for prior treatment provided it is clearly documented to be the appropriate standard-of-care treatment for that tumor type (eg, if listed in NCCN Guidelines).
 - i. Neoadjuvant or adjuvant chemotherapy after primary resection will not be counted as a treatment line if disease progression occurred ≥ 6 months following completion of chemotherapy. If disease progression occurred < 6 months following completion of chemotherapy, the line of therapy will be counted.
 - ii. No more than 1 prior platinum-containing chemotherapy line for advanced disease is permitted. A change of platinum chemotherapy within the same treatment regimen will be considered 1 prior platinum-containing chemotherapy. Patients must not have had radiologic disease progression within 3 months of initiating platinum-containing chemotherapy and must have best response of SD or better.

- iii. Platinum-containing chemotherapy given as radio-sensitization combined with radiation therapy to control locally advanced disease will not be considered as a prior regimen of systemic therapy.
 - iv. Prior combined chemotherapy and radiotherapy is permitted provided the patient has measurable disease outside the radiation field or disease in the irradiated field has progressed.
7. Have sufficient archival formalin-fixed paraffin-embedded (FFPE) tumor tissue for planned analyses. In the event archival tumor tissue is not available, a screening biopsy sample must be collected and provided to the central laboratory, unless the biopsy procedure is considered unsafe or the biopsy site is considered inaccessible by the investigator. Cytospin blocks from ascites are not acceptable.
8. Have adequate organ function confirmed by the following laboratory values obtained within 14 days prior to randomization:
 - a. Bone Marrow Function
 - i. Absolute neutrophil count (ANC) $\geq 1.5 \times 10^9/L$;
 - ii. Platelets $\geq 100 \times 10^9/L$; and
 - iii. Hemoglobin ≥ 9 g/dL independent of transfusion ≤ 14 days prior to screening hemoglobin assessment.
 - b. Hepatic Function
 - i. Aspartate aminotransferase (AST) and alanine aminotransferase (ALT) $\leq 3 \times$ upper limit of normal (ULN). If liver metastases are present, then $\leq 5 \times$ ULN;
 - ii. Total bilirubin $\leq 1.5 \times$ ULN; $< 2 \times$ ULN if hyperbilirubinemia is due to Gilbert's syndrome; and
 - iii. Serum albumin ≥ 30 g/L (3.0 g/dL).
 - c. Renal Function
 - i. Serum creatinine $\leq 1.5 \times$ ULN; or
 - ii. Estimated glomerular filtration rate (GFR ≥ 45 mL/min using the Cockcroft Gault formula; or
 - iii. Measured creatinine clearance (CL_{cr}) ≥ 30 mL/min.
9. Have an ECOG performance status of 0 to 1.
10. Have a life expectancy of at least 4 months.
11. Human immunodeficiency virus (HIV)-infected patients on effective anti-retroviral therapy with undetectable viral load within 6 months of the initiation of antiviral therapy are eligible for this trial, unless the anti-retroviral therapy interferes with rucaparib (see Concomitant Medications section).
12. For patients with evidence of chronic hepatitis B virus (HBV) infection, the HBV viral load must be undetectable within 6 months of the initiation of antiviral therapy on suppressive therapy, if indicated. Patients with a history of hepatitis C virus (HCV) infection must have been treated and cured. Patients with HCV infection who are currently on treatment are eligible if they have an undetectable HCV viral load within 6 months of the initiation of antiviral therapy. Concurrent anti-HBV or anti-HCV

treatment should not interfere with rucaparib treatment (see Concomitant Medications section).

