7.3.4.2 Clinical Laboratory Investigations

Samples for hematology, clinical chemistry, urinalysis, and serum/plasma hCG pregnancy test will be analyzed by a local laboratory. The panels of laboratory tests to be performed are shown below in [Table 6](#).

Laboratory tests will be assessed for all patients at screening, during treatment per the Schedule of Assessments, at the EOT Visit, and Safety Follow-up Visit(s), and if toxicities are present.

Hematology and clinical chemistry results must be reviewed by the investigator before the start of rucaparib and throughout the study. Fasting is not required before blood sampling for clinical chemistry tests. Additional and more frequent tests may be performed at the investigator's discretion.

Table 6. Laboratory Tests

Hematology	Clinical Chemistry	
Red blood cell (RBC) count	Total protein	Glucose
Hemoglobin	Albumin	Sodium
Hematocrit	Creatinine (eGFR) ^a	Potassium
MCV	Blood urea nitrogen (BUN) or urea	Magnesium
MCH	Bilirubin (total, direct, indirect)	Chloride
MCHC	Alkaline phosphatase (ALP)	Bicarbonate (CO ₂ /HCO ₃ ⁻)
Reticulocyte count	Alanine aminotransferase (ALT)	Calcium
White blood cell (WBC) count	Aspartate aminotransferase (AST)	Phosphorus
Differential with absolute neutrophil count (ANC)	Lactate dehydrogenase (LDH)	Lipid panel (Total cholesterol, LDL, HDL, triglycerides)
Platelet count		

Abbreviations: eGFR = estimated glomerular filtration rate; HDL = high-density lipoprotein; LDL = low-density lipoprotein; MCH = mean corpuscular hemoglobin; MCHC = mean corpuscular hemoglobin concentration; MCV = mean corpuscular volume.

^a Estimated GFR using the Cockcroft Gault formula or institutional standard formula may also be collected, as clinically applicable

Urinalysis: Performed locally on a freshly voided clean sample by dipstick for protein, glucose, blood, pH, and ketones. If dipstick findings are abnormal based on the investigator’s judgment, then a microscopic evaluation will be performed to assess the abnormal findings. Urinalysis will be performed at screening (within 14 days prior to first rucaparib dose), during treatment per the Schedule of Assessments, at the EOT Visit, and Safety Follow-up Visit(s).

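### Inclusion criteria 11 and 12 count the undetectable viral load from the start of antiviral therapy, so they do not test whether HIV, HBV or on-treatment HCV is controlled at study entry.

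*Combined protocol and SAP*

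**What the plan says.** Section 4.2 has three viral-load conditions, and all count from the same event.

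- **HIV (criterion 11):** infected patients on effective therapy with "undetectable viral load within 6 months of the initiation of antiviral therapy are eligible for this trial".
- **Chronic HBV (criterion 12):** "the HBV viral load must be undetectable within 6 months of the initiation of antiviral therapy on suppressive therapy, if indicated".
- **HCV under treatment (criterion 12):** patients "currently on treatment are eligible if they have an undetectable HCV viral load within 6 months of the initiation of antiviral therapy".

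Past HCV is handled separately and without a window: "Patients with a history of hepatitis C virus (HCV) infection must have been treated and cured". The Synopsis repeats the three timed conditions in the same terms, so it does not correct the main text.

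Section 4.5 requires every criterion to be met and bars both investigator and sponsor from making exceptions. On testing, Section 7.3.4.2 states: "Samples for hematology, clinical chemistry, urinalysis, and serum/plasma hCG pregnancy test will be analyzed by a local laboratory". Neither the Schedule of Assessments (Table 5) nor the laboratory list (Table 6) includes a viral load for any of the three viruses.

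**The concern.** An eligibility rule on viral infection in an oncology trial normally asks whether the infection is under control when study treatment starts. The words effective (HIV) and suppressive (HBV) suggest the same purpose here. The time clause asks something else: whether the virus became undetectable soon after antiviral therapy began. The two questions can have different answers for the same patient, in either direction.

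Two things are at stake. The first is a safety-relevant entry condition in a trial of a drug for which Section 1.1.7 lists raised transaminases and hematologic toxicity among the most common Grade 3 or higher events. The second is consistency: sites that apply the apparent intent and sites that apply the text will enroll different patients, and the first group will commit eligibility deviations. Some suitable patients, in a population that is already rare, could be turned away.

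**Working it through.** The documents give no figure to reproduce, so the check applies the written rule to test records.

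**Inputs.** The three timed conditions in criteria 11 and 12 (Section 4.2 and Synopsis); the no-exception rule in Section 4.5; the test lists in Tables 5 and 6; the liver limits in inclusion 8b; exclusion 12.

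**The two rules.** Let *S* be the start of antiviral therapy, *U* the date of an undetectable result, and *E* the date of enrollment or first dose.

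- Rule as written: met if some *U* satisfies *U* − *S* ≤ 6 months. *E* does not appear.
- Rule that tests current control: met if the most recent result before *E* is undetectable and *E* − *U* ≤ *L*, where *L* is a look-back period set by the sponsor.

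**Test records.** Where the last column says met, a result within *L* is assumed to be on file.

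| Record | Rule as written | Current control |
|---|---|---|
| A. HBV, undetectable at month 4, detectable at screening | Met (4 ≤ 6) | Not met |
| B. HIV, same course as A | Met (4 ≤ 6); only the undefined word effective stands against entry | Not met |
| C. First undetectable at month 9, suppressed since | Not met (9 > 6); no waiver | Met |
| D. Undetectable at month 4, suppressed since | Met (4 ≤ 6) | Met |
| E. Chronic HBV, no therapy indicated | Cannot be applied: *S* does not exist | Depends on what the sponsor intends |

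Records A and B can pass the viral-load test without current control. Record C fails despite it. Record D is classified correctly. Record E cannot be classified.

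**Does another requirement supply the missing test?**

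- Inclusion 8b limits AST and ALT to 3 × ULN (5 × ULN with liver metastases), with limits on bilirubin and albumin as well. Its reference point is entry: "laboratory values obtained within 14 days prior to randomization" (the study has no randomization, but the direction is clear). It measures liver function, not viremia.
- Exclusion 12 lets the investigator exclude a patient for another condition that raises risk or clouds interpretation. It is a matter of judgment and prompts no measurement. It can keep out record A but cannot admit record C.
- Effective and suppressive therapy are not defined by a result or a date.
- Tables 5 and 6 schedule no viral load.

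**How many patients.** The documents give no prevalence. If 1% to 4% of the maximum 220 patients had one of the three infections (an assumption), 0.01 × 220 = 2.2 and 0.04 × 220 = 8.8, or about 2 to 9 patients. That range counts patients subject to the rule. Those misclassified are a subset, which could be empty.

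**The case against.** The strongest reply is that the clause should not be read alone. A patient with HIV rebound is not plainly on effective therapy, the HBV sentence says the load must be undetectable in the present tense, and exclusion 12 and inclusion 8b remain available. Much of this stands. A reader might infer that nothing else in the protocol would stop a viremic patient; the documents do not support that. What remains is that none of these guards requires a current viral-load result and none can admit a patient who fails the window.

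A second reply is that windows tied to prior therapy are this protocol's normal style. This is correct: many windows in criterion 6 run from earlier treatment, including progression within three months of starting platinum. A reader might infer that criteria 11 and 12 are anomalous because other timed checks count back from entry, and that inference fails. The difference is one of purpose. Criterion 6 asks about treatment history, such as platinum sensitivity, for which a past reference point is apt. Criteria 11 and 12 appear to ask about present control.

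Third, a reader might infer that hepatitis flares would be counted as drug-induced liver injury. Section 8.9 requires that no other cause be immediately apparent and names viral hepatitis, and footnote d of Table 3 calls for evaluation of viral hepatitis. No false-signal rate can be derived from the documents.

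Fourth, the HCV part is thin. Past HCV must be cured, and the window reaches only patients still on treatment.

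**Conclusion.** The concern holds as a defect of wording with consequences for eligibility. The stated viral-load test does not refer to study entry for HIV, HBV or on-treatment HCV. It can be met by a patient whose HBV has rebounded, it fails a patient first suppressed after month 6, and it cannot be applied to chronic HBV with no therapy indicated. It does not follow that long-suppressed patients in general are shut out: one whose virus was undetectable by month 6 passes.

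The effect is small in numbers: at most a handful of patients under the assumed prevalence, with the misclassified share unknown. The response-rate endpoint, the futility rule and the sample size do not depend on it. The conclusion rests on a literal reading, which Section 4.5 invites by allowing no exceptions, and on taking effective and suppressive as evidence that current control is intended. The sponsor can confirm or correct that second point.

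**What to change.** In criteria 11 and 12, in both Section 4.2 and the Synopsis, replace the reference to the start of antiviral therapy with a reference to study entry: the most recent viral-load result before enrollment or first dose of rucaparib must be undetectable, within a look-back period that the sponsor selects and states. The sponsor should also state how criterion 12 applies to chronic HBV when no therapy is indicated. That is a clinical eligibility decision, and no rule is proposed here.

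The cost is a wording change in two places, which can go into an amendment. The downside is that an occasional patient will need a more recent result on file before enrolling.
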